8.4 Packaging and Labeling

Lenalidomide will be packaged in bottles and each bottle will contain 21 capsules.

The label(s) for IP will include sponsor name, address and telephone number, the protocol number, IP name, dosage form and strength (where applicable), amount of IP per container, lot number, expiry date (where applicable), medication identification/kit number, dosing instructions, storage conditions, and required caution statements and/or regulatory statements as applicable. Additional information may be included on the label as applicable per local regulations.

In Germany, rituximab intravenous formulation packaging and label will be provided as investigational product.

8.5 Investigational Product Accountability and Disposal

An accurate accounting of the dispensing/return of study drug for each study subject will be maintained in source documents on an ongoing basis by a member of the study site staff. Additionally, if any study drug is lost or damaged or if the study subject misses a dose, this information should be documented in the study subject's CRF and source documents.

Celgene (or designee) will review with the investigator and relevant site personnel the process for Investigational Product return, disposal, and/or destruction including responsibilities for the site vs. Celgene (or designee).

8.6 Investigational Product Compliance

For the oral medication lenalidomide, study personnel will review the dosing instructions with the subject prior to dispensing the study drug. The subject will be instructed to return the study drug bottle, including any unused study drug, to the site at the next visit. Subject compliance will be noted on the appropriate CRFs and source records based on a capsule count. To monitor treatment compliance, the reconciliation of capsules will be done at the beginning of each Cycle and at treatment discontinuation.
9 CONCOMITANT MEDICATIONS AND PROCEDURES

9.1 Permitted Concomitant Medications and Procedures

Therapies considered necessary for the subject's well being may be administered at the discretion of the investigator. All prescription and over-the-counter medications, treatments and therapies which are related to an adverse event or are clinically relevant from 28 days prior to the start of the study drug through the last dose of study drug must be recorded on the appropriate page of the CRF.

9.1.1 Tumor Flare Reaction Treatment

Treatment of TFR is up to the discretion of the investigator, depending upon the severity and clinical situation. It is suggested that Grades 1 and 2 TFR be treated with NSAIDs (ie, ibuprofen 400 to 600 mg orally every 4 to 6 hours as needed), corticosteroids, and/or narcotic analgesics for pain management. Refer to Table 2 for further instructions and dose modifications for Grade 3 and 4 TFR.

In mild to moderate (Grades 1 and 2) cases, it is suggested that study drug be continued along with symptomatic treatment as above. In more severe cases, study drug should be interrupted, as indicated in Table 2.

During the Treatment Phase, emergency use of corticosteroids at any dose to treat TFR symptoms for a subject is allowed at the investigator's discretion.

9.1.2 Thromboembolism Prophylaxis

It is not known whether prophylactic anticoagulation or anti-platelet therapy prescribed in conjunction with lenalidomide may lessen the potential for venous thromboembolism. The decision by the investigator to take prophylactic measures should be made carefully after an assessment of an individual subject's underlying risk factors.

As reference information, for subjects receiving lenalidomide in open-label trials, it is strongly recommended that subjects with VTE risk receive either aspirin (70 – 325 mg PO daily) or another prophylaxis agent while on lenalidomide. In those subjects with high risk of VTE, it is strongly recommended that the subject receive a prophylactic anticoagulation therapy with low molecular weight (LMW) heparin, or heparin (dose recommended for the prophylaxis of DVT/PE per the package insert) or warfarin (to maintain an International Normalized Ratio [INR] of 2.0). The choice of VTE prophylaxis agent relies upon the investigator's discretion and should be tailored to the subject's individual risk/benefit profile by taking into account the individual thrombotic risk, bleeding risk, and the quality of compliance with the VTE prophylaxis.

9.1.3 Growth Factors

Growth factors (e.g., G-CSF, erythropoietin) may be prescribed by the investigator for rescue from severe hematologic events and should be used in accordance with the American Society of Clinical Oncology's (ASCO) guidelines or the ESMO guidelines.

Growth factors or platelet transfusions should not be administered during the Screening Period to increase a subject's blood values in order to meet entry criteria and are not to be administered

prophylactically, except for high-risk subjects in accordance with the ASCO guidelines or the ESMO guidelines.

9.2 Prohibited Concomitant Medications and Procedures

Systemic chronic corticosteroid use at doses above 20 mg/day (prednisone or equivalent) is prohibited during the Treatment Phase. For subjects receiving systemic corticosteroids at doses above 20 mg/day (prednisone or equivalent), a 7-day washout period prior to Cycle 1 Day 1 study drug dosing is required.

Systemic doses above 20 mg/day (prednisone or equivalent) are allowed for the treatment of TFR at any time, for rituximab cytokine release syndrome prophylaxis with each rituximab infusion on Cycle 1 Day 1, and treatment of infusion-related reactions at any time.

In addition, short courses of steroids are permitted at high doses for short-term use if necessary for the well being of the subject. Examples of such short-term use include the treatment of exacerbation of chronic obstructive pulmonary disease and other conditions for which short-term steroid treatment is considered standard of care.

9.3 Required Concomitant Medications and Procedures

9.3.1 Tumor Lysis Syndrome Prophylaxis

All subjects at risk for TLS should receive TLS prophylaxis (allopurinol, rasburicase or equivalent as per institutional guidelines) and be well hydrated (orally) during the first week of the first Cycle or as clinically indicated. Hydration levels should be adjusted according to age and clinical status. To monitor for TLS, the subjects will have a complete blood count (CBC) and chemistry drawn on Days 1, 8, and 15 of the first Cycle and additionally as clinically indicated. The site should make every effort to contact the subject on Day 5 (\pm 1 day) of the first Cycle to inquire about the subject's condition and to make sure that he/she is continuing with TLS prophylaxis measures by keeping hydrated and taking the TLS prophylaxis as instructed per investigator discretion. Any subject contact that is made on Day 5 (\pm 1 day) should be documented in the subject's medical record, and any AEs that are discovered should be captured on the CRF. TLS will be assessed by the Cairo-Bishop Grading system (see Appendix D).

9.3.2 Rituximab Premedication

Premedication consisting of acetaminophen and an antihistamine should be administered before each rituximab infusion (see package insert). Steroids may also be administered before the start of the rituximab infusion according to institutional practice (see Section 9.2 for the permitted doses). Surveillance measures during and after infusion of rituximab and infusion rate should be applied as recommended by the manufacturer/current guidelines.

10 STATISTICAL ANALYSES

10.1 Overview

The objective of the statistical analyses is to compare the efficacy and safety of lenalidomide plus rituximab combination maintenance therapy (for 18 cycles) followed by optional lenalidomide single-agent maintenance (to progression) versus rituximab single-agent maintenance (for 18 cycles) after 12 cycles of induction therapy with lenalidomide plus rituximab in subjects with relapsed/refractory follicular lymphoma grades 1-3b, transformed follicular lymphoma, marginal zone lymphoma, or mantle cell lymphoma.

All statistical analyses specified in this protocol will be conducted using SAS® version 9.2 or higher.

10.2 Study Population Definitions

The following three populations, defined as below, will be used in the analysis.

Intent-to-treat (ITT) population: The ITT population is defined as all subjects who are randomized and have received at least one dose of maintenance therapy.

The ITT population will be used for the primary efficacy analysis. Subjects will be analyzed according to the treatment arm to which they are initially assigned.

Modified Intent-to-treat (mITT) population: The mITT population is defined as all subjects who satisfy the following conditions:

- 1) are randomized
- 2) have received at least one dose of maintenance therapy
- 3) have confirmed diagnosis of relapsed/refractory FL grades 1-3b, transformed FL, MZL, or MCL
- 4) have SD, PR or CR/CRu after completing induction therapy
- 5) have at least one tumor assessment for efficacy after beginning of maintenance therapy

The efficacy analysis will also be performed on the mITT population as supportive evidence and/or sensitivity analysis. Subjects will be analyzed according to the treatment arm to which they are initially assigned.

Safety population: The safety population is defined as all subjects who have received at least one dose of study drug, including induction therapy. The safety population will be used for all safety analyses. For safety analysis of the maintenance period, subjects will be analyzed according to the treatment that they actually received.

Induction Efficacy Population: The Induction Efficacy Population is defined as all subjects who meet all of the criteria for eligibility into the study.

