10.6.1 Primary Efficacy Endpoint

Progression-free Survival

The primary efficacy endpoint for the study is PFS, which is defined as the time from the first dose date of maintenance therapy to objective disease progression or death from any cause, whichever occurs first. The PFS events will be determined using a modification of the IWG 1999 criteria (Cheson, 1999).

Subjects who did not experience disease progression and who did not die before the clinical data cut-off date will be censored at the time of the last visit with adequate response assessment when the subjects were known not to have progressed. Subjects who received new anticancer therapy without objective disease progression will be censored at the date of the last radiological assessment prior to the new anticancer therapy.

The primary efficacy endpoint will be compared between the two treatment arms when 114 PFS events that happen after the first dose date of maintenance therapy are observed.

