10.6.2 Secondary Efficacy Endpoint

Secondary efficacy endpoints will include OS, IOR, ORR, CRR, DOR, DOCR, TTNLT and TTHT.

Overall Survival

The OS is defined as the time between the first dose date of maintenance therapy and death from any cause. Subjects who complete the study and are still alive at the time of the clinical data cutoff date will be censored at the last visit date or the last contact date, whichever is later. Subjects who were lost to follow-up prior to the clinical data cut-off date will also be censored at the time of the last contact. Overall survival information will be collected for 5 years from the date of the last subject initiating induction therapy. The additional OS data may be analyzed as supplementary information. No formal hypothesis testing will be performed post the final primary endpoint analysis.

Improvement of Response

Improvement of response is defined as the proportion of subjects who have improved their tumor response during the maintenance phase, that is, the proportion of subjects who are converted from PR at the end of induction period to CR/CRu as best response, and subjects who are converted from SD at the end of induction period to PR or better as best response during the maintenance phase.

Overall Response Rate

Overall response will be analyzed in two aspects. The overall response rate at the end of 18 cycles of maintenance therapy is defined as the proportion of subjects with a response of at least PR (including CR, Cru, and PR) by the end of 18 cycles of maintenance therapy and prior to any treatment change.

In addition, best ORR, defined as the proportion of subjects with a best response of at least PR (including CR, CRu and PR) after the first dose date of maintenance therapy and prior to any treatment change, will also be presented.

Complete Response Rate

Complete response will also be analyzed in two aspects. The complete response rate at the end of 18 cycles of maintenance therapy is defined as the proportion of subjects with a response of at least CRu (including CR and CRu) by the end of 18 cycles of maintenance therapy and prior to any treatment change.

In addition, best CRR, defined as the proportion of subjects with a best response of at least CRu (including CR and CRu) after the first dose date of maintenance therapy and prior to any treatment change, will also be presented.

Duration of Response

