Duration of response is defined only for subjects who have achieved PR or better after the first dose date of maintenance therapy and prior to any treatment change. It is calculated as the time from the initial response (at least PR) after the first dose date of maintenance therapy and prior to treatment change to documented disease progression or death.

Subjects who have not progressed or died at the time of the clinical data cutoff date will be censored at the last assessment showing no progression. Subjects who change treatment without evidence of disease progression will be censored at the last assessment showing no progression prior to treatment change.

Duration of Complete Response

Duration of complete response is defined only for subjects who have achieved CR/CRu after the first dose date of maintenance therapy and prior to any treatment change. It is calculated as the

time from the initial response (at least CRu) after the first dose date of maintenance therapy and prior to treatment change to documented disease progression or death.

Subjects who have not progressed or died at the time of the clinical data cutoff date will be censored at the last assessment showing no progression. Subjects who change treatment without evidence of disease progression will be censored at the last assessment showing no progression prior to treatment change.

Time to Next Anti-lymphoma Treatment

Time to next anti-lymphoma treatment is defined as the time from the first dose date of maintenance therapy to the time of first documented administration of new anti-lymphoma therapy. Subjects without new treatment therapy will be censored at the last visit.

Time to Histological Transformation

Time to histological transformation is defined as the time from the first dose date of maintenance therapy to the time of histological transformation as measured based on documentation of histological transformation (as assessed by the investigator). In case of clinical suspicion of transformation, including rapid disease progression, unexpected changes in "B" symptoms or rapidly increasing LDH, a biopsy should be performed. In this clinical trial, histological transformation will be considered disease progression. This endpoint will not be calculated for subjects randomized with transformed Follicular Lymphoma (tFL).

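### The set labelled ITT admits only randomised subjects who took a maintenance dose, so no efficacy comparison in the readable text covers everyone randomised to maintenance

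*Combined protocol and SAP*

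**What the plan says.** Section 10.2 (Study Population Definitions): "The ITT population is defined as all subjects who are randomized and have received at least one dose of maintenance therapy". This set carries the primary analysis, by assigned arm. The mITT set repeats the dose condition and adds others, among them a tumour assessment after maintenance has begun, so it is a subset. Section 10.6 puts all efficacy analyses on the first set and repeats them on mITT to assess robustness. The only other sensitivity analyses named, in Section 10.6.4, are unstratified tests.

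The endpoints in Sections 10.6.1 and 10.6.2 are tied to the same dose or to the maintenance phase:

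- PFS is "defined as the time from the first dose date of maintenance therapy to objective disease progression or death from any cause". The final comparison is made when "114 PFS events that happen after the first dose date of maintenance therapy are observed".
- OS: "The OS is defined as the time between the first dose date of maintenance therapy and death from any cause".
- Next treatment: "Time to next anti-lymphoma treatment is defined as the time from the first dose date of maintenance therapy". Time to histological transformation has the same origin.
- Best ORR and best CRR: "after the first dose date of maintenance therapy and prior to any treatment change, will also be presented".
- DOR: "It is calculated as the time from the initial response (at least PR) after the first dose date of maintenance therapy". DOCR is built the same way.
- IOR: "Improvement of response is defined as the proportion of subjects who have improved their tumor response during the maintenance phase".

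The safety population and the disposition summary (Section 10.5) do reach non-starters, but neither compares their PFS or OS by arm. The Induction Efficacy Population is defined by eligibility and is not tied to a comparison of the maintenance arms.

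**The concern.** Randomisation follows induction (Sections 4.1.4 and 8.3), so every subject randomised under the current design belongs in the comparison of maintenance arms. Requiring a dose selects subjects after randomisation. The trial is open-label and progression is judged by the investigator, so the arm is known before the first dose and could influence whether a subject starts.

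If it does, and those who do not start differ in prognosis, the dosed sets are no longer comparable. The hazard ratio and the type I error then move, in either direction. The mITT analysis drops the same subjects, so it would agree with a biased result instead of exposing it. The ITT label tells readers that this selection has not been made.

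**Working it through.** **1. The plan's own figures.** Section 10.3 calls a hazard ratio of 0.533 20% better than assumed, so the assumed value is 0.533/0.8 = 0.666. At one-sided 0.025, 1:1:

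- Events for 80% power: 4 × (1.960 + 0.842)² / (ln 0.666)² = 191, as stated.
- Power at 114 events, Φ(|ln HR| × √114/2 − 1.960): 58.2% at 0.666 (plan: 57.9%) and 91.9% at 0.533 (plan: 92%).

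The design figures reproduce. They do not bear on who is excluded, except that the events themselves are counted only after the first dose.

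**2. Size of a possible bias, by hand.** Suppose there is no true effect, the same share of each arm has *m* times the hazard, and each arm loses the stated part of that share.

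- A 6% v B 3%, *m* = 3: dosed Arm A keeps no high-hazard subjects; dosed Arm B keeps 3/97 = 3.1%. Initial hazard ratio: 1/(1 + 0.031 × 2) = 0.942.
- A 3% v B 1%, *m* = 2: Arm B keeps 2/99 = 2.0%. Initial hazard ratio: 1/1.020 = 0.980.

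High-hazard subjects have their events first, so the ratio then drifts towards 1.

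**3. Simulation over the whole follow-up.** From the plan: 157 per arm (314/2), 63 months' entry, 5% annual dropout, 114 events. Assumed: uniform entry, exponential PFS with median 60 months, unstratified log-rank at 1.96, interim ignored. There were 100,000 runs per row.

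| Undosed, A v B | Hazard of non-starters | Median HR | One-sided error |
|---|---|---|---|
| none | – | 1.00 | 0.025 |
| 5% v 5% | 3x | 1.00 | 0.025 |
| 8% v 0% | 1x | 1.00 | 0.025 |
| 3% v 1% (about 5 v 2 subjects) | 2x | 0.984 | 0.031 |
| 6% v 3% (about 9 v 5 subjects) | 3x | 0.962 | 0.040 |
| 1% v 3% | 2x | 1.016 | 0.021 |
| 3% v 6% | 3x | 1.039 | 0.015 |
| 8% v 0% (extreme) | 3x | 0.906 | 0.076 |

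The error follows from the hazard ratio. For 0.962, |ln HR| × √114/2 = 0.0387 × 5.339 = 0.207, and Φ(0.207 − 1.960) = 0.040. With a median of 40 or 90 months, the 6% v 3% case gives 0.963 and 0.039–0.040; the 3% v 1% case gives 0.985–0.986 and 0.029–0.031.

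**4. What inclusion recovers for PFS.** Section 6.3 stops scans once new anti-lymphoma therapy starts without progression, and Section 10.6.1 censors PFS at the last radiological assessment before it. All-randomised result in the 6% v 3%, 3x case, by the share of non-starters who switch at once:

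| Switch at once | HR | One-sided error | Non-starter events among 114 |
|---|---|---|---|
| none | 1.00 | 0.025–0.026 | 9.5 |
| half | about 0.98 | 0.030–0.032 | 4.9 |
| all | about 0.96 | 0.038–0.040 | 0 |

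**5. Power cost of inclusion.** If a share *u* of Arm A is undosed and does as control, HR = (1 − *u*) × 0.666 + *u*. For *u* = 2%: 0.98 × 0.666 + 0.02 = 0.673, power 56.2%. For 4%: 0.680, 54.1%. For 8%: 0.693, 49.9%. If those subjects also have three times the hazard, simulated power is 54.4%, 51.6% and 45.8%.

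**The case against.** The best defence is that the excluded group is probably small and similar in both arms. One dose of either drug keeps a subject in the set, and both arms are due rituximab on Cycle 13 Day 1 (Section 8.2). Nothing in the documents records a randomised subject who never started. Section 8.2.4.5 may look like evidence of loss, but it describes postponement until the event resolves, after which the cycle begins; such a subject is dosed and stays in. All of this stands, and it limits the weight of the point.

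An entry condition also has a reason for subjects randomised before induction under the 16 January 2014 version, since some may never have reached maintenance. That holds for them, but not for subjects randomised at the end of induction.

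It is also fair to say that inclusion is no complete cure. Step 4 shows that non-starters who switch therapy at once add nothing to PFS under the plan's censoring rule. The benefit for OS remains, because Section 10.6.2 does not censor OS at new therapy.

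A reader might infer that subjects are analysed by treatment received. They are not: Sections 10.2 and 10.6 keep the assigned arm. The fault lies in the exclusion and the time origin.

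**Conclusion.** The point holds as a defect of definition. In the readable text, the primary set, the supportive set and the time-to-event origins all depend on a maintenance dose, so no efficacy comparison covers all subjects randomised to maintenance and no planned check would reveal an effect of leaving out non-starters.

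The size and direction of any effect are unknown. Equal loss, or loss unrelated to prognosis, does no harm. Modest unequal loss with worse prognosis in Arm A would give a hazard ratio of 0.96 to 0.98 under no effect and an error of 0.03 to 0.04; the reverse pattern makes the test conservative. These figures rest on assumed shares and hazards.

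A reader might infer that the type I error is in fact inflated, or that the trial favours Arm A. The documents do not support that: they give no non-starter counts, and the shared rituximab dose argues against large differences. Nor can one say that no all-randomised analysis exists anywhere. Section 4.4 refers to a Statistical Analysis Plan, but no separate SAP text and no Section 10.6.3 can be read.

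**What to change.** 1. **Analysis set.** If no data have been compared by arm, define ITT as all subjects randomised to maintenance at the end of induction, dosed or not, analysed as randomised. Time PFS, OS, TTNLT and TTHT from randomisation, and count the 95 interim and 114 final events on that set. Rename the present set the dosed (as-randomised) set and keep it as a sensitivity analysis. If the interim has already been run on the dosed set, keep that set as primary under its accurate name so that alpha spending stays coherent. Then pre-specify the all-randomised analysis from randomisation as the key sensitivity analysis before final data are compared by arm.
2. **New therapy.** State how the PFS censoring rule applies to non-starters, and add a PFS sensitivity analysis that counts the start of new therapy as an event.
3. **Response endpoints.** Keep undosed subjects in the denominators of IOR, ORR and CRR as non-responders unless a response is documented after randomisation and before new therapy. Open the window for qualifying responses at randomisation, but leave DOR and DOCR running from initial response.
4. **Subjects randomised before induction.** Requiring SD or better is selection after randomisation. Report these subjects apart from the ITT set, or include them under a different label with a stated origin and repeat the primary analysis without them.
5. **Reporting.** Tabulate non-starters by arm and reason. This would show whether the issue is material.

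**Cost.** Wording in Sections 10.2, 10.3, 10.6 and 10.8, and a few extra runs. Event counts must be reconciled: if non-starters stay under follow-up, they supply about 4 (3% v 1%, 2x) to 10 (6% v 3%, 3x) of the 114 events, leaving about 110 to 104 in the dosed set. Power falls from about 58% to 56% if 2% of Arm A is undosed and does as control. Enrolled subjects are already followed for progression (Sections 4.1.4 and 6.3), so no new schedule is needed. The change is late and must be documented as made without knowledge of results by arm. If the interim has been run, the primary set and its event counts stay as they are, and the cost falls to renaming, the table and the sensitivity analyses.
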